receptors on pain perception have produced conflicting results: no effect on pain [21-24], increased pain following high dose and decreased pain at low dose naloxone[25-28]. The same contradictory findings are true for several rodent studies [29-32]. To our knowledge, the ratings in the human studies were all unitary measures of pain intensity. However, a more recent study on this topic [33] utilized rating systems for both pain unpleasantness and pain intensity allowing the authors to differentiate the affective component of pain. The opioid blockade significantly increased pain unpleasantness ratings of experimental pain but the pain intensity ratings remained unaffected [33]. Our aim is to replicate this finding and add to it brain imaging data (fMRI) to characterize the brain areas associated with producing this dichotomized pain perception. By deciphering this neuronal process we could potentially also understand how mood can alter pain unpleasantness independent of pain intensity [34], if understood these components strengthen therapeutic strategies for treatment of chronic pain using mood altering therapies.

2. Study Objectives

Hypothesis 1 (primary outcome): Participants will experience a significant increase in the pleasantness but not intensity of cutaneous brushing and deep skin/muscle pressure after administration of naloxone (compared to saline).

Hypothesis 2 (secondary outcome): Participants will experience a significant increase in the unpleasantness but not intensity of cutaneous heat pain after naloxone administration.

Hypothesis 3 (secondary outcome): The effect of endogenous opioids on perception will be partially mediated by changes in mood, with negative mood increasing the pleasantness of pleasant touch and increasing the unpleasantness of pain.

Hypothesis 4 (secondary outcome): Stimulus-evoked neural activations will be modulated by naloxone administration, with preferential effects in cingulate cortex and insula.

3. Subjects

a. Description of study populations

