Functional scan: Each participant will be scanned on a 3T MRI scanner using a standard head coil. During each session, two fMRI scans (containing multiple runs) will be collected using a blood oxygenation level-dependent (BOLD) protocol with a T2*-weighted gradient echo planar

imaging (EPI) sequence. During the functional scans heart rate, blood oxygenation, and respiration rate will be monitored. We will use a 3D MP-RAGE (Magnetization Prepared Rapid Acquisition by Gradient Echo) T1-weighted sequence for the anatomical scan. Including the functional and anatomical scan, subjects will be continuously in the scanner for approximately 75 min (see Figure1).

Visual Analogue Scales

Separate scales (see Attachment 3) will be used to assess sensory intensity/pain, unpleasantness/pleasantness, mood, and anxiety at baseline and throughout each session using a computer presentation method. Participants will use a mouse to log their ratings. Pain intensity will be assessed on a scale ranging from no sensation (-100) to pain threshold (0), to intolerable pain (100). Sensory hedonics (unpleasantness vs. pleasantness) will be assessed on a scale ranging from extremely unpleasant (-100) to neutral (0), to extremely pleasant (100). Mood will be assessed on a scale ranging from extremely bad mood (-100) to neutral mood (0), to extremely good mood (100), anxiety will be assessed on a scale ranging from extreme anxiety (-100) to neutral (0) to extreme calm (100), wanting will be assessed on a scale ranging from not at all (-100), to neutral (0), to very much (100) and liking will be assessed on a scale ranging from not at all (-100), to neutral (0), to very much (100). These scales have been used previously to separate the intensity and hedonic components of pain perception (eg.[39] [40]).

Questionnaires

Participants will fill out several questionnaires before or after the first test session: the Temperament and Character Inventory (TCI), which includes dopamine-related traits [41], the Behavior Appetitive System Scale (BAS) [42], the Hospital Anxiety and Depression Scale (HADS) to evaluate anxiety [43], the NEO Personality Inventory [44], and the Social Touch Scale [45]. If there is not sufficient time to complete all questionnaires during the first session, those questionnaires will be completed during another session of the study. At the end of each session participants will be asked whether they believe they received saline or naloxone that day.

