All data will be assessed for normality of distribution using the Shapiro Wilk W test. A significant W statistic indicates that the hypothesis of a normal distribution should be rejected, i.e. a significant W indicates skewed data. If the data is skewed the data transformation method will be chosen based on the distribution (Box-Cox method) of the dependent variable. The resulting transformed data will be analyzed with parametric statistics. In the descriptions below we will describe the parametric statistical tests. If data transformation does not work, non-parametric tests will be applied.

Behavioral Data

All behavioral data will be analyzed using SPSS or similar statistical package. A significance level of $p < 0.05$ will be adopted for all analyses.

For the primary and secondary outcomes, we will use paired t-test to evaluate the drug effect. To determine whether the effect of drug on touch pleasantness is mediated by mood, we will use Wager & Lindquist's Multilevel Mediation and Moderation (M3) Toolbox. In the analysis, the dependent variables are the sensory ratings, the independent variable is the drug and the mediator variable is mood.

MRI data will be analyzed using standard brain imaging packages such as FSL or AFNI. For the initial analysis, the individual performing the analysis will be blinded. Whole brain analysis will be the first analysis performed followed by analysis looking at individual activations (parameter

estimates) in regions of interest including the insula, cingulate cortex and orbitofrontal cortex. These activations will be used to conduct a mediation analysis of these brain areas in mediating the effect of drug on touch pleasantness ratings. In this analysis, the dependent variables are the perceptual ratings, the independent variable is the level of stimulus and the mediator is the BOLD activation in the brain area of interest (ROI).

b. Power analysis

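### Hypotheses 1 and 2 predict a rise in the affective rating without a rise in intensity, but no planned analysis compares the two drug effects, and brushing intensity has no clearly assigned test

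*Combined protocol and SAP*

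**What the plan says.** Section 2 states two-part hypotheses. Hypothesis 1 expects a "significant increase in the pleasantness but not intensity of cutaneous brushing" and of deep pressure; Hypothesis 2 expects a "significant increase in the unpleasantness but not intensity of cutaneous heat pain after naloxone administration".

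For heat the dissociation is itself an aim. Section 1 describes an earlier study in which "the pain intensity ratings remained unaffected [33]. Our aim is to replicate this finding", and adds imaging to "characterize the brain areas associated with producing this dichotomized pain perception". Section 4d (Visual Analogue Scales) says of the rating scales: "These scales have been used previously to separate the intensity and hedonic components of pain perception".

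Section 9 makes pleasantness of light stroking the primary outcome. The secondary outcomes name affect and/or intensity for deep pressure and for heat pain. Brushing intensity is not listed there, although the précis mentions intensity of light brush among its comparisons.

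For the primary and secondary outcomes, Section 10a says "we will use paired t-test to evaluate the drug effect", at p<0.05. For skewed data it adds: "If data transformation does not work, non-parametric tests will be applied". The other analyses are mediation models, by mood and by brain activation. Section 10b sizes the study on pleasantness alone.

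**The concern.** A significant result for one rating and a non-significant result for another does not show that the two drug effects differ. The plan contains no drug-by-rating contrast, no equivalence margin and no interval rule. The mediation models do not fill the gap, because they ask what carries a drug effect or a stimulus effect, not whether two drug effects are unequal.

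If naloxone moved both heat ratings by the same amount, chance alone could yield the predicted pattern. It could then be reported as selective for unpleasantness, and the imaging would be interpreted as explaining a dissociation that was never tested. For brushing the gap is wider, because the intensity rating has no clearly assigned test.

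**Working it through.** **Inputs from the documents.** 24 completers, d = 0.61 for the pleasantness change, 80% power, alpha 0.05, 20% dropout (Section 10b); a paired t-test (Section 10a). Both ratings come from the same people in a crossover.

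**Assumed, because the documents do not give them.** Effect sizes for intensity and for heat; correlation between the two drug effects within a person (0, 0.3, 0.5, 0.7); equal SDs unless stated; two-sided tests.

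**1. The plan's own figure.** Noncentral t with df = 23 and noncentrality 0.61 × √24 = 2.99 against a critical value of 2.069 gives power 0.816. At n = 23 power is 0.798. So 24 reproduces, and 24/(1 − 0.2) = 30.

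**2. What a non-significant intensity test can show.** The 95% CI half-width is 2.069/√24 = 0.42 SD, and 0.42/0.61 = 0.69. A null estimate therefore leaves room for an effect about two-thirds the size of the planned one.

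| True intensity effect (SD) | Power at n=24 | Non-significant |
|---|---|---|
| 0.3 | 0.291 | 71% |
| 0.4 | 0.467 | 53% |
| 0.5 | 0.650 | 35% |

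**3. The predicted pattern when no dissociation exists.** Bivariate normal drug effects, n = 24, 100,000-200,000 simulated trials per cell, both true effects equal. Chance that the affective test is significant and the intensity test is not:

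| Both effects (SD) | corr 0 | 0.3 | 0.5 | 0.7 |
|---|---|---|---|---|
| 0.3 | 0.207 | 0.171 | 0.144 | 0.110 |
| 0.4 | 0.250 | 0.202 | 0.170 | 0.130 |
| 0.5 | 0.227 | 0.188 | 0.157 | 0.120 |
| 0.61 | 0.150 | 0.129 | 0.109 | 0.085 |

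**4. Adding a direct contrast.** Test the within-person difference of the two drug effects, with the hedonic scale sign-reversed so that more unpleasant is positive. With equal SDs its standardised effect is (d1 − d2)/√(2 − 2ρ). Claim selectivity only if both the affective test and this contrast are significant in the same direction. In the cells of step 3 the false-claim rate is 1.5-2.5% on raw points and 2-5% if each effect is divided by its own trial SD.

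**5. Scaling matters when SDs differ.** If both ratings move by the same number of points but the intensity SD is 1.5-2 times larger, the rule claims selectivity in 0.3-2.5% of trials (raw points) against 5-43% (own SD). If the standardised effects are equal and the intensity SD is two-thirds as large, the rates are 6-26% (raw) against 2-5% (own SD). Each rate is an error only under the stated meaning of equal.

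**6. What the rule costs when the effect is truly selective.**

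| True effects, affect v intensity | Pattern in step 3 | Rule, one scaling (raw) | Rule, both scalings agree |
|---|---|---|---|
| 0.61 v 0, equal SDs | about 78% | 51-79% | 48-78% |
| 0.4 v 0, equal SDs | 44% | 22-37% | – |
| 0.4 v 0, intensity SD × 1.5 | 44% | – | 14-19% |

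Ranges run from correlation 0 to 0.7; a dash means that no figure is quoted.

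**The case against.** - *The plan never says that p>0.05 will be read as no effect.* This is correct. A reader might infer that the plan commits to that error, but no section does so, and the outcome wording in the précis and Section 9 is neutral. What stands is that the plan supplies no other basis for the intensity half of the hypotheses.
- *The primary analysis is sound.* This is also correct. The primary outcome is pleasantness of stroking alone, and 24 reproduces. A reader might infer that the sample size or the primary test is compromised; neither is.
- *The misreading rate is modest.* At the only documented effect size, 0.61 and for pleasantness, it is 8-15%. The 25% end needs an assumed 0.4 SD effect and zero correlation. The range should be quoted with those conditions.
- *The scales are not directly comparable.* The intensity scale puts zero at pain threshold and the hedonic scale puts it at neutral. This stands for heat as well as touch, so no single scaling is authoritative and the choice must be declared. Heat still warrants a formal contrast, because the dissociation is an aim there and the plan cites these scales as separating the components of pain.
- *Changing to a comparative claim alters the hypothesis.* This is fair. The investigators may keep the hypothesis as Section 2 states it, but then they need an equivalence margin.

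**Conclusion.** The concern holds in a limited form. The stated tests cannot support the conclusion that naloxone changes affect but not intensity. For brushing, the intensity half has no clearly assigned test at all. With 24 completers an intensity effect of 0.3-0.5 SD is missed in 71% down to 35% of trials. A spurious dissociation appears in 8-15% of trials if both effects are 0.61 SD, and in up to 25% if they are smaller. These figures rest on assumed effects, correlations of 0-0.7, equal SDs and normality.

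A reader might also infer that Hypothesis 1 should become a comparative claim. That would leave it without a confirmatory test, since the plan has none for touch. Nor do the documents establish that there is still time to fix the rule blind. Section 4d covers the experimenter and participants, and Section 10a covers the initial imaging analyst. The behavioural analyst's blinding and the study's stage are not stated.

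**What to change.** 1. **Section 10a, all stimuli.** Report every intensity effect, including brushing intensity, with its 95% CI. State that a non-significant intensity test will not be read as no effect.
2. **Heat (Hypothesis 2).** Claim selectivity for unpleasantness only if the unpleasantness effect is significant and the paired within-person contrast of the two drug effects, hedonic scale sign-reversed, is significant in the same direction. Choose raw points or standardised effects before the behavioural analyst sees treatment codes, and show the other as a sensitivity analysis. If the transformation or non-parametric fallback is used, put both ratings on the same scale or transformation. In Section 2, either reword to a rise in unpleasantness greater than that in intensity, or keep the absence claim with a pre-set equivalence margin.
3. **Brushing and pressure (Hypothesis 1).** Limit the tested hypothesis to the rise in pleasantness. Report intensity and the contrast descriptively with CIs, because the two scales have different anchors.

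The cost is a few sentences in Sections 2 and 10a, using ratings already collected. The price is more inconclusive selectivity results, by the amounts in the last table of the working. The loss is small if the two drug effects are strongly correlated, and large if the heat effect is modest or intensity is the noisier rating.

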AFNI = Analysis of Functional NeuroImages

1. Introduction and Background

A better understanding of the human endogenous opioid system and its innate activation mechanisms is important for unraveling the neurochemical underpinnings of alternative therapies for depression, anxiety and pain. Here, we investigate the role of endogenous opioids in affective dimensions of touch and pain with the hypothesis that this system modulates the pleasantness of touch and the unpleasantness of pain.

Since brain regions rich in opioid receptors, such as the insula, cingulate cortex and orbitofrontal [1], are activated by a subtype of unmyelinated sensory afferents (C low-threshold mechanoreceptor; C-LTMR) which respond particularly well to slow gentle stroking of the skin

and that this type of touch is perceptually pleasant ([2, 3]), it is likely that endogenous opioids are released by this stimulus. Primate studies have previously shown that monkeys both solicit and receive more grooming after opioid blockade ([4]; [5]; [6]; [7]; [8]), suggesting an increased wanting or liking of social touch under reduced opioid levels. Similarly, in humans, we have some preliminary evidence that pleasantness ratings of gentle skin stroking increase after opioid blockade by naloxone [9], suggesting that reduced opioid levels actually make touch more pleasant and desirable. However, it is not clear whether the perceptual effect of blocking endogenous opioids is due to a direct effect of opioids on the sensory pathways or is an indirect effect caused by the opioids modulating mood and mood in turn modulating touch perception [10]. The possibility of the indirect effect is supported by data showing that opioid blockade leads to a negative mood state [11]; [12]; [13]. One theoretical hypothesis is that a negative mood state increases the hedonic value of social touch [10].

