Consent will be obtained before any study procedures will be done. Upon arrival at the Clinical Center, the participant will be assigned a CRIS identification number through the NIH Admissions Office. The consent form will be explained and all questions will be answered before the participant is asked to sign the consent form (see Section 14 for details). Consent may occur during an additional, separate visit from the subsequent two research sessions.

Participants eligible to proceed will be asked to undergo two testing sessions, separated by at least 1 day, in the NIH Clinical Research Center's Functional MRI Facility (FMRIF, Building 10, Room B1D307 or B1D305). Each participant will receive naloxone on one day, and saline on the other, with drug order counterbalanced across subjects. At each visit, a urine sample will be collected from all participants for drug screening. In addition, at each visit, participants who are able to become pregnant will also take a urine pregnancy test. Date of onset for previous menstrual cycle will be documented to allow for later analysis of confounds of menstrual cycle in perceptual outcomes. Medical inclusion and exclusion criteria will be reviewed with the participant at the beginning of each study session to confirm continued eligibility. The participants will have their intravenous line placed before any part of the fMRI will start. A baseline scan including data collection for all sensory conditions will be collected before the intravenous infusion. Drug infusion will then start with a bolus injection followed by a continuous infusion of naloxone or saline and the full sensory paradigm will be repeated. An anatomical MRI will also be acquired.

Sensory testing paradigm

Sensory testing will occur on the participant's left lower leg. While it is most common for brushing paradigms to brush on the hairy skin on the arm (C-LTMR fibers primarily innervate

hairy skin), several studies have reported the same preference for slow, C-LTMR brushing on the leg [35], including the shin [36]. According to our unpublished data the calf is also a site of high pleasantness ratings for deep compression, and more accessible in the MRI scanner. We will therefore conduct all sensory testing on subjects' lower leg. Participants will be asked to wear shorts or change into scrubs for each session in order to access the lower leg.

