During each period of fMRI recording (before and after drug infusion) we will administer six stimulus blocks (approx.5 min each). Each block will contain only one type of stimulus (fast or slow brushing, high or low pressure, high or low heat), with stimuli lasting 10-30 sec and inter-stimulus-intervals of at least 15 sec. Gentle brushing will be performed at two speeds (~3cm/s and ~30 cm/s) using a soft brush. A trained experimenter blind to the drug condition will administer the brushing, using audio or visual cues to keep the correct rate of brushing. Since the subject will be in the MRI scanner throughout all stimulation, the experimenter will not be visible to the subjects, thus eliminating interpersonal cues. Deep pressure will be administered using an inflatable compression cuff designed by the NIH Clinical Center machine shop. Similar to a blood pressure cuff, the inflatable cuff will wrap around the participant's lower leg and will inflate to a pleasant pressure and a less pleasant pressure (both less than 120 mmHg). Heat stimuli will be administered by the trained experimenter using a contact thermode (Medoc Pathway System; Medoc Ltd., Advanced Medical System, Israel). Heat will be approximately 46°C (painful) and approximately 41°C (non-painful). Similar painful heat stimuli have been used in our lab and elsewhere, including in approved NIH protocols [37].

After each stimulus block, subjects will provide ratings of pain intensity, unpleasantness/pleasantness, bad mood/ good mood, anxiety/calm, wanting and liking (see below and Attachment 2). We will use stimulus presentation software such as e-prime or matlab for stimulus presentation and recording of ratings. NRS ratings of current ongoing pain and discomfort will be taken after functional MRI scans.

Drug Administration

All study participants will receive both drug conditions (naloxone and saline), one at each experimental session. Both substances will be administered intravenously by licensed providers. For naloxone, to achieve a constant plasma level throughout the ~45 min testing phase, a bolus

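### Mood is rated with pleasantness after each block, so the planned mood mediation cannot tell mood changing perception from perception changing mood; the bias can mask Hypothesis 3 for touch and imitate it for pain

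*Combined protocol and SAP*

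**What the plan says.** Section 4.d (Sensory testing paradigm) runs each scan period as single-stimulus blocks: "we will administer six stimulus blocks (approx.5 min each". The rating set that follows includes the hedonic scale and mood: "After each stimulus block, subjects will provide ratings of pain intensity, unpleasantness/pleasantness, bad mood/ good mood, anxiety/calm, wanting and liking". Section 4.d (Visual Analogue Scales) adds that scales are used for "mood, and anxiety at baseline and throughout each session using a computer presentation method". The readable text specifies no mood rating between the start of the drug and the first post-drug stimulus.

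Hypothesis 3 (Section 2) expects partial mediation by mood, "with negative mood increasing the pleasantness of pleasant touch and increasing the unpleasantness of pain". Section 1 supplies the expected first link, citing data that "opioid blockade leads to a negative mood state". Section 10.a (Behavioral Data) gives the model: "In the analysis, the dependent variables are the sensory ratings, the independent variable is the drug and the mediator variable is mood". It names a multilevel mediation toolbox, but no lag, no time ordering, no reverse-path model and no sensitivity analysis.

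**The concern.** A mediator has to act before the outcome. Here mood is recorded after about five minutes of the stimulus, in the same rating set as the hedonic score, so it may already reflect how pleasant or unpleasant the block was. A pre-infusion mood rating cannot stand in, because it cannot carry a drug effect.

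The likely direction of the bias can be worked out on the hedonic scale (-100 extremely unpleasant, +100 extremely pleasant). Feedback from perception to mood gives a positive slope: a more pleasant block improves mood and a more unpleasant one worsens it. Hypothesis 3 needs a negative mood-to-rating slope for touch and a positive one for pain. Feedback therefore opposes the hypothesis for touch and resembles it for pain.

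What is at stake is the question Section 1 leaves open: whether opioid blockade acts directly on the sensory pathways or indirectly through mood.

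**Working it through.** **The plan's own figure.** Section 10.b gives d = 0.61, power 80%, alpha 0.05 and n = 24. For a two-sided paired t-test the noncentrality is 0.61 × √24 = 2.99. Power is 0.816 at n = 24 and 0.798 at n = 23, so 24 reproduces. Allowing for 20% dropout, 24 / 0.8 = 30. This figure concerns the total drug effect on pleasantness. No figure is given for the mediation test.

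**Inputs for the mediation check.** From the documents: n = 24, a within-subject crossover, drug as X, mood as M, rating as Y, and the signs of Hypothesis 3. Assumed, because the documents give no values (all in SD units of naloxone-minus-saline differences):
- drug effect on mood a = -0.6, and also 0;
- touch: true mood slope b = -0.4, direct drug effect c = +0.4;
- pain: true mood slope b = 0, direct drug effect c = -0.6 (more unpleasant);
- reverse slope r = 0 to 0.4.

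**Model.** True mood difference M0 = a + u. Rating difference Y = c + b·M0 + e. Mood as recorded after the block M = M0 + r·Y. The errors u and e are independent with SD 1. The analysis regresses Y on M and declares mediation when the drug-to-mood and mood-to-rating paths both have two-sided p < 0.05.

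**Expected estimates.**
- Mood-to-rating slope = [b(1 + rb) + r] / [(1 + rb)² + r²].
- Drug-to-mood effect = a + r(c + ab).

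Example, touch at r = 0.3: 1 + rb = 0.88. The slope is (-0.352 + 0.3) / (0.7744 + 0.09) = -0.06, against a true -0.40. The drug effect on recorded mood is -0.6 + 0.3 × (0.4 + 0.24) = -0.41.

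Example, pain at r = 0.3: the slope is 0.3 / 1.09 = 0.28, against a true 0. The drug effect on recorded mood is -0.6 - 0.18 = -0.78, or -0.18 if a = 0.

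**Results** (slopes from the formula, percentages from simulation):

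| Reverse slope r | 0 | 0.1 | 0.2 | 0.3 | 0.4 |
|---|---|---|---|---|---|
| Touch: estimated slope (true -0.40) | -0.40 | -0.30 | -0.19 | -0.06 | +0.07 |
| Touch: mediation declared, a = -0.6 | 36% | 18% | 8% | 3% | 2.5% |
| Pain: estimated slope (true 0) | 0 | 0.10 | 0.19 | 0.28 | 0.34 |
| Pain: false mediation, a = -0.6 | 4% | 6% | 13% | 26% | 42% |
| Pain: false mediation, a = 0 | 0.2% | 0.4% | 1% | 3% | 7.5% |

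The last row is small because both paths must be significant. With a = 0 the drug-to-mood path comes only from feedback, at most 0.4 × 0.6 = 0.24 SD.

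**Second model, with simultaneous feedback** (M = aX + rY + u, Y = cX + bM + e, a = -0.61). For touch with b = -0.5 and c = 0.305, reverse slopes of 0/0.1/0.2/0.3/0.5 give detection of 50/31/17/8/1%. For pain scored as unpleasantness, with b = 0 and c = 0.61, the same sizes of slope with negative sign give false mediation in the direction of Hypothesis 3 of 2/6/13/26/59%. The pattern is the same.

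**The case against.** **A time-ordered rating may already exist.** Section 10.a says only that the mediator is mood. Section 4.d describes ratings throughout the session, the telephone script describes mood ratings as ongoing, and the session timeline is in Figure 1, which is not shown. A reader might infer that no post-drug, pre-stimulus rating is taken. The readable text cannot establish that. Blocks also run in sequence, so five of the six post-drug blocks follow an earlier post-drug rating. This stands, and it limits the point to an analysis of the concurrent ratings, which is all that the readable plan describes.

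**The size is assumed.** A reader might infer that the timing alone will hide mediation for touch and manufacture it for pain. The documents do not support that. They give no reverse slope and no size for the mood effect, and one cited study (reference 23) reports in its title that naloxone did not alter mood. At r = 0.1 the touch slope is attenuated, not reversed, and false pain mediation barely moves (6% against 4%), although touch detection still halves. Substantial false pain mediation within this range of r also needs a real drug effect on mood: at a = -0.3 it is about 7/16/27% for r = 0.2/0.3/0.4.

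**The crossover removes part of the problem.** Any effect of a stimulus on mood that is the same under naloxone and saline cancels in the drug contrast. That is correct, but feedback from a drug-altered hedonic response remains, and the model above already works on paired differences. Counterbalancing ("Each participant will receive naloxone on one day, and saline on the other, with drug order counterbalanced across subjects") protects the total drug effects on mood and on ratings. It gives no direction to the path between them.

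**The model is not the planned analysis.** One difference score per person is a stand-in for a multilevel mediation model, so the percentages are illustrative.

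**Conclusion.** The point holds in conditional form. Mediation estimated from mood and hedonic ratings made together cannot separate mood changing perception from perception changing mood, and Section 10 does not require any other rating. If perception feeds back on mood, the bias opposes Hypothesis 3 for touch and mimics it for pain. Under the stated assumptions the consequence ranges from modest at a reverse slope of 0.1 to severe at 0.3 or more. For pain it is severe mainly if naloxone itself lowers mood, which Section 1 expects but does not quantify.

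The scope is Hypothesis 3 only, which is listed as secondary in Section 2 and as tertiary in Section 9.c. A reader might carry the doubt over to the main result, but the primary paired t-test and the sample size of 24 do not use the mediator and are unaffected.

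**What to change.** - Show the existing mood and anxiety scales immediately before each block or, at minimum, once after the bolus and before the first post-drug block. If the schedule in Figure 1 already contains such a rating, use it.
- Name that rating as the mediator in Section 10.a.
- If no rating can be added, use mood from the preceding block and adjust for that block's stimulus type. Block order is not stated in the readable text, and a heat block may carry over into the mood recorded before a touch block. The first post-drug block would have no usable prior rating.
- State the path signs Hypothesis 3 requires: naloxone lowers mood, with a negative mood slope for touch and a positive one for pain on the hedonic scale. A significant result with other signs should not count as support.
- Report mediation from concurrent post-block mood as associational only.

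The cost is a few seconds per block and a few sentences in Section 10. A pre-stimulus rating will correlate less with the outcome, so the indirect effect may look smaller. Power also stays limited: even with no feedback, detection in the touch example is about 36% at n = 24. Time ordering removes the reverse path, but mood is still not randomised, so other common causes of mood and ratings remain.
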